4.5.2.2 Incidence rate analysis

Follow-up adjusted incidence rate for the placebo-controlled period will be summarized by system organ class and preferred terms both by treatment group and by treatment group stratified by ApoE status.

Final V1.0

4.5.2.3 Subgroup analysis for protocol version 4

Due to the change in maximal dose from 6 mg/kg to 10 mg/kg for ApoE &4 carrier high dose group in protocol version 4, not all subjects have had opportunity to receive the protocol specified high dose (6 doses in titration before receive 10mg/kg) in the placebo-controlled period. Incidence tables of AEs and SAEs will be provided for ApoE &4 carriers who were randomized to the high dose group, stratified by the expected number of doses at 10 mg/kg (categories of 0, 1-6, 7-13, 14, and a total column of having at least one dose) a subject would have received based on the first infusion date and the date consenting to protocol version 4. Randomization treatment groups will be used for this analysis.

4.5.3 ARIA – AE of special interest

4.5.3.1 Background

ARIA is an AE of special interest in this study. Please see protocol section 7.2.1 for ARIA management and dose disposition guidelines. Since ARIA is a brain MRI finding, ARIA data are collected under two data sources: (1) safety MRI data as recorded on brain MRI worksheet by central MRI reader; (2) AE eCRF. For each ARIA event, the information of start/end date, severity, locations in brain regions and status on MRI scan is collected on the brain MRI worksheet by central MRI reader. ARIA severity is determined by central MRI reader based on number and size of the ARIA regions on imaging. An AE record is then entered into the eCRF by the investigator with the start/end date and severity information from brain MRI worksheet, and with information on the symptomatic status and action taken towards study drug. If ARIA is symptomatic, the symptoms will be entered into AE eCRF and the severity of the symptoms will be determined by the investigator. AE eCRF data will be used as the primary source for ARIA analysis as it contains the complete information of ARIA as well as associated symptoms. Safety MRI data will also be used to show the consistency between two data sources, provide details on MRI assessments, and for any specific analysis that requires information from MRI.

ARIA includes ARIA-E (vasogenic edema) and ARIA-H (hemorrhage). ARIA-H includes ARIA-H microhemorrhage, ARIA-H macrohemorrhage and ARIA-H superficial siderosis. Table 6 shows the reported term on MRI worksheet, the corresponding reported term on AE eCRF, and the MedDRA preferred term and lower level term for each type of ARIA.

Table 6: Reported and MedDRA terms for ARIA

Reported term on MRI worksheet	Reported term on AE eCRF	MedDRA version 21.0 preferred term	MedDRA version 21.0 lower level term
ARIA-E	Asymptomatic ARIA-E Symptomatic ARIA-E	Amyloid related imaging abnormality-oedema/effusion	ARIA-E

Final V1.0

ARIA-H microhemorrhage	Asymptomatic ARIA-H (Microhemorrhage) Symptomatic ARIA-H (Microhemorrhage)	Amyloid related imaging abnormality-microhaemorrhages and haemosiderin deposits	ARIA-H
ARIA-H macrohemorrhage	Asymptomatic ARIA-H (Macrohemorrhage) Symptomatic ARIA-H (Macrohemorrhage)	Amyloid related imaging abnormality-microhaemorrhages and haemosiderin deposits	ARIA-H
ARIA-H superficial siderosis	Asymptomatic ARIA-H (Superficial Siderosis) Symptomatic ARIA-H (Superficial Siderosis)	superficial siderosis of the central nervous system	superficial siderosis of the central nervous system

For any specific ARIA event, the start date of the duration based on MRI is the date of the MRI assessment that initially identifies the ARIA event, and the end date of the duration based on MRI is the date of the MRI assessment that shows the complete resolution of this ARIA event (in the case of ARIA-E), or the date of the MRI assessment that shows ARIA being stable (in the case of ARIA-H). Stable was defined as 'No change' or 'decrease' in number, size, severity or number of locations between 2 consecutive MRIs including the initial detection MRI and the follow-up MRIs.

For symptomatic ARIA events, if there is any related symptom that proceeds the first MRI identification, then the symptom onset date will be used as the start date of the symptomatic ARIA duration. The end date of the symptomatic ARIA duration will be the date of the resolution or stable MRI as defined above for the duration based on MRI.

If the severity increases, or the event changes from asymptomatic to symptomatic, or from non-serious to serious, more than one AE records will be added to eCRF to capture the change with new start/end AE dates (the end date of the previous record will be the start date of the next record). For analysis, records with changes in severity or symptomatic status or seriousness are considered as a single ARIA event. The severity/symptomatic status/seriousness for that event is defined as the worst level among all the AE records that belong to that event.

If the same type of ARIA event happens again after the previous event has ended, then it is considered a recurrent event of ARIA of that type. Recurrent events will be referred as the second event, the third event, and etc.

If the duration based on MRI of an ARIA-E event overlaps with the duration based on MRI of an ARIA-H event, then these 2 ARIA events are considered as concurrent events.

Final V1.0

4.5.3.2 Incidence and summary of ARIA

Incidence of ARIA-E, ARIA-H, ARIA-E and ARIA-H (not necessarily concurrent), concurrent ARIA-E and ARIA-H, ARIA-E or ARIA-H, isolated ARIA-H (only ARIA-H, no ARIA-E), ARIA-H microhemorrhage, ARIA-H macrohemorrhage and ARIA-H superficial siderosis will be summarized based on both AE eCRF and MRI data. If there is any discrepancy in incidence between the two data sources, a listing of the subjects and ARIA events with discrepancy will be provided. In addition, the incidence table based on AE eCRF source will also be done by treatment group (placebo, low dose, high dose and BIIB037 total; analysis display A in Appendix 6.1).

Number of subjects with each type of ARIA, maximum severity and worst symptomatic status of the type of ARIA being analyzed will be summarized based on AE eCRF. For subjects with symptomatic ARIA, the maximum severity of symptoms will also be summarized.

Number of subjects with ARIA-H microhemorrhage events post-baseline (broken down by categories of 1-4, 5-9 and >=10) stratified by whether they have had microhemorrhage at baseline will be summarized based on safety MRI data. The summary will be conducted based on the MRI that shows the maximum number of microhemorrhages as well as the last MRI in the study period.

Summary of concurrent ARIA-E and ARIA-H will be provided including the following information: number of subjects with concurrent ARIA-E and ARIA-H (and further broken down to each type of ARIA-H), the severity of ARIA-E based on MRI, the symptomatic status of ARIA-E, the severity of symptoms based on AE eCRF. For subjects with recurrent ARIA-E events, if there is an event concurrent with ARIA-H, it will be used for the summary, and the first concurrent event will be used if there are more than one event concurrent with ARIA-H.

An incidence table of AEs considered by the investigator to be related to ARIA by system organ class and preferred term for subjects with symptomatic ARIA will be provided, as well as a listing of these AEs. Similarly, an incidence table of AEs related to ARIA for subjects with symptomatic ARIA and severe symptoms will be provided, as well as a listing of these AEs.

Listings of AE records for each type of ARIA events and listings of MRI assessments for subjects with each type of ARIA events will be provided.

Montreal Cognitive Assessment (MOCA) is performed at baseline and at each unscheduled ARIA monitoring visit for ARIA subjects (approximately every 4 weeks) except for mild asymptomatic microhemorrhage subjects. An incidence table of subjects with ARIA events whose MOCA total scores decrease 2 points or more from baseline will be provided. A listing of MRI assessments and MOCA total scores for subjects with ARIA events will be provided.

Line plots of MMSE mean change from baseline values and standard errors at each planned visit (baseline, Week 26, Week 50 and Week 78) will be provided by treatment group stratified by ApoE status and with stratification on the following factors:

(1) ARIA-E severity based on MRI. The groups are: subjects without ARIA-E, subjects with mild ARIA-E, subjects with moderate ARIA-E and subjects with severe ARIA-E.

Final V1.0

(2) Within ARIA-E subjects, stratify by the severity of the concurrent symptoms based on AE eCRF. The groups are: subjects without symptoms, subjects with mild symptoms, subjects with moderate symptoms, and subjects with severe symptoms.

For subjects with recurrent ARIA-E events, the first ARIA-E event will be used for the classification for each of the factors.

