3.5.3.2 Incidence and summary of ARIA

Incidence of ARIA-E, ARIA-H, ARIA-E and ARIA-H (not necessarily concurrent), concurrent ARIA-E and ARIA-H, ARIA-E or ARIA-H, isolated ARIA-H (only ARIA-H, no ARIA-E), ARIA-H microhemorrhage, ARIA-H macrohemorrhage and ARIA-H superficial siderosis in the LTE period and in the placebo-controlled and LTE active treatment period will be summarized based on both AE eCRF and MRI data. If there is any discrepancy in incidence between the two data sources, a listing of the subjects and ARIA events with discrepancy will be provided. In addition, the incidence table based on AE eCRF source will also be done by LTE treatment group (analysis display A in Appendix 4.1).

Number of subjects with each type of ARIA, maximum severity and worst symptomatic status of the type of ARIA being analyzed in the LTE period and in the placebo-controlled and LTE active treatment period will be summarized based on AE eCRF. For subjects with symptomatic ARIA, the maximum severity of symptoms will also be summarized.

Summary of concurrent ARIA-E and ARIA-H will be provided including the following information for the LTE period and for the placebo-controlled and LTE active treatment period: number of subjects with concurrent ARIA-E and ARIA-H (and further broken down to each type of ARIA-H), the severity of ARIA-E based on MRI, the symptomatic status of ARIA-E, the severity of symptoms based on AE eCRF. For subjects with recurrent ARIA-E

Final V1.0

events, if there is an event concurrent with ARIA-H, it will be used for the summary, and the first concurrent event will be used if there are more than one event concurrent with ARIA-H.

An incidence table of AEs considered by the investigator to be related to ARIA by system organ class and preferred term for subjects with symptomatic ARIA in the placebo-controlled and LTE active treatment period will be provided, as well as a listing of these AEs. Similarly, an incidence table of AEs related to ARIA for subjects with symptomatic ARIA and severe symptoms will be provided, as well as a listing of these AEs.

Listings of AE records for each type of ARIA events and listings of MRI assessments for subjects with each type of ARIA events will be provided.

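### The concurrent ARIA-E/ARIA-H summary grades each subject by the first concurrent episode, so it can understate but never overstate the worst one, and no other concurrent-only table shows the worst

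*SAP*

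**What the plan says.** Section 4.5.3.2 of the placebo-controlled SAP plans a summary of concurrent ARIA-E and ARIA-H. It counts the subjects and then describes their ARIA-E by "the severity of ARIA-E based on MRI, the symptomatic status of ARIA-E, the severity of symptoms based on AE eCRF". When a subject has recurrent ARIA-E, an event that overlaps with ARIA-H is chosen over one that does not. If several overlap, "the first concurrent event will be used if there are more than one event concurrent with ARIA-H". LTE SAP section 3.5.3.2 has the same sentence ("first concurrent event will be used if there are more than one event concurrent with ARIA-H"), applied both to the LTE period and to the combined active treatment period.

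Three other provisions bear on this:

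- **By-type ARIA table, section 4.5.3.2.** It reports, per subject, "maximum severity and worst symptomatic status of the type of ARIA being analyzed will be summarized based on AE eCRF". For subjects with symptomatic ARIA it adds the maximum severity of symptoms.
- **Grading of a single event, section 4.5.3.1.** "The severity/symptomatic status/seriousness for that event is defined as the worst level among all the AE records that belong to that event".
- **Separation of events, section 4.5.3.1.** "If the same type of ARIA event happens again after the previous event has ended, then it is considered a recurrent event".

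**The concern.** ARIA is the adverse event of special interest in this study, and the concurrent summary is the one planned table that links how severe ARIA-E was to the presence of ARIA-H. It selects the episode by order, not by grade. A subject with a mild, asymptomatic first concurrent episode and a severe, symptomatic second one enters the table as mild and asymptomatic.

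This can happen only in subjects with at least two concurrent episodes. Any understatement therefore tends to fall on groups with more recurrent ARIA-E, and on the LTE, which lasts up to 5 years and gives recurrences more time to accrue. A reader who uses the table to judge the worst ARIA-E seen alongside ARIA-H would get an answer that is either right or too mild, with nothing in the table to tell which.

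**Working it through.** The SAP states no figure on this point, so there is none to reproduce. The check sets the provisions side by side.

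**1. Direction.** The first concurrent event is one member of the set of a subject's concurrent events. The worst grade over a set is at least as bad as the grade of any member. On each attribute, the table therefore equals or understates the subject's worst concurrent grade and cannot overstate it. The total number of subjects with concurrent ARIA is the same under either rule.

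**2. A hypothetical subject.** Two ARIA-E events both overlap with ARIA-H. The first is mild and asymptomatic, the second severe and symptomatic.

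| Planned output | What it shows for this subject | Restricted to, or split by, concurrence with ARIA-H? |
|---|---|---|
| Concurrent summary (4.5.3.2) | mild, asymptomatic | yes |
| By-type maximum table (4.5.3.2) | severe, symptomatic | no; pools concurrent and non-concurrent ARIA-E |
| Per-event counts (4.5.3.3) | one mild and one severe event; the severe one also among symptomatic events, with symptom severity | no |
| Second/third-event table (4.5.3.3) | second event severe, symptomatic, with SAE status | no |
| Listings (4.5.3.2, 4.5.3.3) | all records | only if the reader matches ARIA-E and ARIA-H dates by hand |

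The severe episode is reported, but no table shows that it was concurrent with ARIA-H.

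**3. Conventions elsewhere in the placebo-controlled SAP.** Several subject-level safety summaries take the worst value:

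- the by-type ARIA table ("maximum severity and worst symptomatic status of the type of ARIA being analyzed");
- the microhemorrhage table in 4.5.3.2, which uses the MRI with the highest count as well as the last MRI;
- the adverse event tables by maximum severity in 4.5.2.1;
- the worst post-baseline laboratory grade in 4.5.4.2.

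First-event selection is used for the MMSE plots in 4.5.3.2 ("the first ARIA-E event will be used for the classification for each of the factors"), where each subject needs one fixed classification. It is also used for the first-ARIA-E table in 4.5.3.3, which is titled accordingly and paired with a table of second and third events. The concurrent summary has no companion table for later concurrent episodes.

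**4. Size.** Let *m* be the share of subjects in the table who have two or more concurrent ARIA-E events. Let *w* be the share of those in whom a later concurrent event is worse than the first on a given attribute. The share of subjects in the table who are under-graded is *m* × *w*, which lies between 0 and *m*. The documents give neither quantity.

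**The case against.** A reader might infer that the table contradicts the SAP's own worst-level rule. It does not. That rule in 4.5.3.1 combines the eCRF records of one event, and the same section treats a recurrence after resolution as a separate event. Choosing among separate events leaves the rule untouched, and the chosen event is still graded at its own worst level.

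A reader might also infer that later severe or symptomatic episodes drop out of the report. They do not: the by-type maximum table, the per-event counts, the recurrence table and the listings all carry them.

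A third temptation is to attach a percentage. That would need an assumed severity split, an assumption of independence between a subject's episodes, and the share of subjects with several concurrent episodes. The documents supply none of these. Correlation within subjects, and the dose adjustments after ARIA that section 2.1 allows, would further weaken an independence assumption.

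The first-event rule also has merits. It is explicit and reproducible, it gives one like-for-like episode per subject, and it keeps all attributes on the same episode. A worst-of-all measure can only rise with more episodes and longer observation, and LTE SAP section 3.5.2.2 itself notes that active periods differ in length between early and late starters. As a description of ARIA-E at first concurrence, the table is accurate.

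All of this stands. It argues for keeping the first-event view, not for omitting the worst concurrent grade from every table. It also means that a remedy should not silently combine the MRI grade of one episode with the symptoms of another.

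**Conclusion.** The point holds as a minor reporting gap in a descriptive table. For subjects with several concurrent ARIA-E events, the summaries in 4.5.3.2 and LTE 3.5.3.2 equal or understate the worst concurrent MRI severity, symptomatic status and symptom severity, and no other planned table restricted to concurrent events fills the gap. It is a difference in convention from the by-type table in the same section, not an internal contradiction.

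The direction follows from the selection rule alone. The size is unknown and may be small, because it depends wholly on how many subjects have two or more concurrent episodes and how often a later one is worse. No hypothesis test is affected, and neither is the total count of subjects with concurrent ARIA.

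**What to change.** In section 4.5.3.2 and LTE section 3.5.3.2:

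1. Keep the present rows and label them as the first concurrent event.
2. Add rows for each subject's worst concurrent ARIA-E event, defined as the one with the highest MRI severity, with symptomatic status and symptom severity taken from that same event.
3. Add separately labelled rows for the worst symptomatic status and worst symptom severity over all of the subject's concurrent events.
4. In the LTE table, footnote that the worst-event rows depend on length of follow-up, which differs between early and late starters.

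The cost is a short text change in each SAP and a few extra table rows, using data already collected. The drawback is the dependence on follow-up. The footnote discloses it, and the retained first-event rows offset it.

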4.5.3.3 Summary of recurrent ARIA-E

Follow-up adjusted incidence rate of subjects with ARIA-E, with 2 or more events of ARIA-E, with 3 or more events of ARIA-E and with more than 3 events of ARIA-E based on their entire follow-up time will be summarized based on AE eCRF. The entire follow-up time is from the first dose until the last day in the placebo-controlled period.

Number of total ARIA-E events and the MRI severity of each event will be summarized based on AE eCRF. Number of total symptomatic ARIA-E events, the MRI severity of each symptomatic event and the severity of the symptoms of each symptomatic event will be summarized based on AE eCRF.

Summary of first ARIA-E events table based on AE eCRF will summarize the number of subjects with a first event of ARIA-E, the MRI severity of the events, the symptomatic status of the events, the severity of the symptoms for symptomatic events, whether SAE or not, number of resolved and unresolved events, duration of the resolved events, time from first infusion in study (active or placebo) to onset, number of doses received since the start of the study to onset, dose level of the last infusion received prior to onset, dosing status (continue as planned, dose interrupted, dose reduced, or dose discontinued) after the events, and the number of subjects with recurrent ARIA-E events. The same summary of first ARIA-E events table will also be done on subjects who had recurrent ARIA-E events.

Summary of recurrent ARIA-E events table based on AE eCRF will summarize the following information for both the second and third event of ARIA-E events: the number of subjects with the previous event of ARIA-E, the number of subjects with at least one dose and one MRI after the previous ARIA-E resolution, the number of subjects with this event of ARIA-E, the MRI severity of the events, the symptomatic status of the events, the severity of the symptoms for symptomatic events, whether SAE or not, number of resolved and unresolved events, duration of the resolved events, time from first infusion in study (active or placebo) to onset, time from previous resolution to onset, number of doses received since the start of the study to onset, dose level of the last infusion received prior to onset, dosing status (continue as planned, dose interrupted, dose reduced, or dose discontinued) after the events. The number of subjects with more than 3 events of ARIA-E, and the number of subjects who discontinued study treatment after recurrent ARIA-E onset will also be summarized.

A listing of subjects who withdrew from the study with unresolved ARIA-E or subjects with ongoing ARIA-E at the time of data cutoff (also considered as unresolved) will be provided with the details of the event including the duration from onset to last follow-up.

For subjects with recurrent ARIA-E, a listing of study drug administration, MRI assessments, severity and symptomatic status of each event, and end-of-treatment reason (if present) will be provided.

Final V1.0

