defined as the number of subjects who experienced an event divided by total number of
subjects in the analysis population, i.e., percentage. Each subject will be counted only
once within each category.

Final V1.0

- Incidence and incidence rate will be provided in incidence rate tables. Two different kinds of incidence rate tables will be provided as appropriate for different analyses. Definitions are provided below.
 - (1) Follow-up adjusted incidence rate defined as the number of subjects who experienced an event divided by the total of entire follow-up time among the subjects in the analysis population. The entire follow-up time for a subject is defined as the time from the first dose until the last day on study. Each subject will be counted only once within each category.
 - (2) Exposure-adjusted incidence rate (EAIR) defined as the number of subjects who experience an event divided by the total exposure adjusted follow-up time among the subjects in the analysis population. The exposure adjusted follow-up time is defined as the time from the first dose until the initial occurrence of the event for those who experienced an event, or from the first dose until the end of follow-up (the last day on study) for those who did not. Each subject will be counted only once within each category.

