4.5.3.4 Exposure adjusted analysis

Exposure adjusted incidence rate of ARIA-E events will be summarized based on safety MRI data. The exposure adjusted follow-up time is from the first dose until the initial occurrence of ARIA-E for those who experienced ARIA-E, and until the end of follow-up for those who did not. Since ARIA is an MRI finding, the day of the last MRI assessment in the placebo-controlled period will be used as the end of follow-up for those who didn't experience the event.

Study drug administration information prior to first ARIA-E onset will be summarized for ARIA-E subjects, including number of total infusions, number of infusions at each dose level (placebo, 1 mg/kg, 3 mg/kg, 6 mg/kg and 10 mg/kg), dose level of the last infusion, maximum dose level received, and cumulative dose as a continuous variable.

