4.5.3.5 Time to event analysis

Kaplan-Meier plot of time to first ARIA-E event will be produced based on safety MRI data. Time to event is calculated as date of the MRI assessment that initially detects ARIA-E event - date of first infusion (aducanumab or placebo) +1. Censor time for subjects without ARIA-E is calculated as date of last MRI assessment in the placebo-controlled period - date of first infusion (aducanumab or placebo) +1. Estimated proportion with ARIA-E and number of subjects at risk at selected timepoints will also be presented. The plot will be presented by treatment group stratified by ApoE status.

4.5.3.6 Subgroup analysis for protocol version 4

Due to the change in maximal dose from 6 mg/kg to 10 mg/kg for ApoE &4 carrier high dose group in protocol version 4, not all subjects have had opportunity to receive the protocol specified high dose (6 doses in titration before receive 10mg/kg) in the placebo-controlled period. Incidence of ARIA events and summary of first ARIA-E events tables will be provided for ApoE &4 carriers who were randomized to the high dose group, stratified by the expected number of doses at 10 mg/kg (categories of 0, 1-6, 7-13, 14, and a total column of having at least one dose) a subject would have received based on the first infusion date and the date consenting to protocol version 4. Randomization treatment groups will be used for this analysis.

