3.5.3.3 Summary of recurrent ARIA-E

Follow-up adjusted incidence rate of subjects with ARIA-E, with 2 or more events of ARIA-E, with 3 or more events of ARIA-E and with more than 3 events of ARIA-E over their entire follow-up time for the placebo-controlled and LTE active treatment period will be summarized based on AE eCRF.

Number of total ARIA-E events in the placebo-controlled and LTE active period and the MRI severity of each event will be summarized based on AE eCRF. Number of symptomatic ARIA-E events in the placebo-controlled and LTE active period, and the severity of the symptoms of each symptomatic event will be summarized based on AE eCRF.

Summary of first ARIA-E events table based on AE eCRF will summarize the number of subjects with a first event of ARIA-E, the MRI severity of the events, the symptomatic status of the events, the severity of the symptoms for symptomatic events, whether SAE or not, number of resolved and unresolved events, duration of the resolved events, time from first active infusion in study to onset, number of doses received since the start of the period to onset, dose level of the last infusion received prior to onset, dosing status (continue as planned, dose interrupted, dose reduced, or dose discontinued) after the events, and the number of subjects with recurrent ARIA-E events. This table will be done on the placebocontrolled and LTE active treatment period. The same summary of first ARIA-E events table will also be done on the subset of subjects who had recurrent ARIA-E events.

Summary of recurrent ARIA-E events table based on AE eCRF will summarize the following information for both the second and third event of ARIA-E events: the number of subjects CONFIDENTIAL

Final V1.0

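### Follow-up adjusted ARIA-E rates count person-time after the last MRI, when no ARIA-E can be recorded, so they are biased downward or at best unchanged (minor)

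*SAP*

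**What the plan says.** Section 4.5.3.3 of the placebo-controlled SAP specifies "Follow-up adjusted incidence rate of subjects with ARIA-E, with 2 or more events of ARIA-E, with 3 or more events of ARIA-E". A further row covers subjects who had over three such events, and the source is the AE eCRF. The section fixes the denominator: "The entire follow-up time is from the first dose until the last day in the placebo-controlled period". This follows the general definition in Section 4.5.1: "The entire follow-up time for a subject is defined as the time from the first dose until the last day on study".

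Two neighbouring analyses of ARIA-E stop earlier for subjects without the event. For the exposure-adjusted incidence rate (EAIR), Section 4.5.3.4 says that "the day of the last MRI assessment in the placebo-controlled period will be used as the end of follow-up", and gives the reason: "Since ARIA is an MRI finding". Section 4.5.3.5 does the same for the Kaplan-Meier plot: "Censor time for subjects without ARIA-E is calculated as date of last MRI assessment in the placebo-controlled period".

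The LTE SAP repeats the split. Its Section 3.5.3.3 takes the rates "over their entire follow-up time for the placebo-controlled and LTE active treatment period", which Section 3.5.2.2 runs to the last day in the study. Its Sections 3.5.3.4 and 3.5.3.5 stop subjects without ARIA-E at the last MRI.

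**The concern.** The reason given in Section 4.5.3.4 is not specific to the EAIR. Using the AE eCRF as the source does not avoid it. Under Section 4.5.3.1 the investigator's record takes its dates and severity from the central reader's MRI worksheet, and an event starts at the scan that first shows it. A symptomatic event may be dated back to symptom onset, but a scan must still identify it. A subject who stays in the study after the last scan is therefore not under observation for ARIA-E, yet keeps adding person-time.

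ARIA is the trial's adverse event of special interest, and these rows are its follow-up adjusted rates. At stake is a downward bias in a safety rate, from time that the SAP itself treats as unobserved two paragraphs later. The first row (any ARIA-E) is affected as well as the recurrence rows.

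**Working it through.** The SAP states no ARIA-E rate or person-time, so there is no figure of its own to reproduce. The check is on direction, and then on size under stated assumptions.

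**Direction.** The numerator is the same under both stopping rules, because every counted event needs a scan. Hence

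rate to last day / rate to last MRI = person-time to last MRI / person-time to last day = 1 − g/T,

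where T is mean time from first dose to last day and g is the mean gap from last MRI to last day. Since g ≥ 0, the planned rate is lower than or equal to the rate over observable time.

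**Inputs.**
- T for an LTE entrant: about 76 + 4 = 80 weeks (Section 2.1).
- T for a subject who completes treatment but does not enter the LTE: about 76 + 18 = 94 weeks (Section 2.1).
- g: assumed. The MRI schedule is left to the protocol.

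**Understatement, 100 × g/T:**

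| Subject | g (weeks) | Rate too low by |
|---|---|---|
| LTE entrant, T = 80 | 0 / 2 / 4 / 8 | 0 / 2.5 / 5.0 / 10.0% |
| Not entering LTE, T = 94 | 0 / 4 / 8 / 16 / 18 | 0 / 4.3 / 8.5 / 17.0 / 19.1% |

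**Mixed cohort**, assuming gaps of 2 weeks (LTE) and 16 weeks (non-LTE). Mean time to last MRI is then 78 weeks in both groups (80 − 2 and 94 − 16).
- 50% enter LTE: T = 0.5 × 80 + 0.5 × 94 = 87.0; 1 − 78/87.0 = 10.3%.
- 70% enter LTE: T = 84.2; 1 − 78/84.2 = 7.4%.
- 90% enter LTE: T = 81.4; 1 − 78/81.4 = 4.2%.

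**What this does not cover.** The rows for 2 or more, 3 or more and more than 3 events also carry person-time from subjects who never had a first ARIA-E, and from the time before a first event resolved. As an illustration only, assume a first event that resolves at Week 36, a last MRI at Week 78, mean follow-up of 84 weeks, and a share f of subjects with ARIA-E. Time at risk of a second event is then f × (78 − 36)/84 = 0.5f of the denominator: 5%, 10% and 17.5% for f = 10%, 20% and 35%. Under these assumptions that dilution is much larger than the one above, and stopping at the last MRI does not remove it.

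**The case against.** Section 4.5.1 defines two different rates. The follow-up adjusted rate runs to the last day and does not stop at the event; the EAIR stops at first occurrence. Section 4.5.3.3 names the first and applies its definition. A reader might infer that the SAP contradicts itself, but it does not. This part of the objection stands. It does not explain the choice of denominator, though: Section 4.5.1 also ends the general EAIR at the last day on study, and Section 4.5.3.4 overrides that default for ARIA-E. Section 4.5.3.3 makes no parallel change and gives no reason.

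A reader might also expect the rates to equal the EAIR once the end date is changed. They would not. The EAIR stops subjects with ARIA-E at first onset and draws on safety MRI data, whereas Section 4.5.3.3 uses the AE eCRF. A Kaplan-Meier proportion would not equal a rate in any case.

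The size is open. A scan at or near the final visit would make the gap close to zero, and nothing in the SAP says that the 18-week safety follow-up is unscanned. Nor does the SAP show that the gap differs by arm. Subjects with ARIA do have extra monitoring visits about every 4 weeks (Section 4.5.3.2), which makes a difference conceivable but not established.

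Finally, no test or decision rests on these rows. Incidence tables, the EAIR and the Kaplan-Meier plot already describe first ARIA-E, the last two within MRI-limited time. Section 4.5.3.3 also counts subjects with a dose and a scan after the previous resolution, which is closer to a true at-risk group for recurrence. All of this limits the consequence without changing the direction of the bias.

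**Conclusion.** The point holds as a minor one. The denominators in Section 4.5.3.3 and LTE Section 3.5.3.3 include time when ARIA-E could not be recorded, so the descriptive rates are biased downward or unchanged.

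The percentages are illustrations, not estimates. They rest on assumed gaps between last scan and last day, on follow-up of about 80 or 94 weeks for subjects who complete treatment, and on assumed shares entering the LTE. Eighteen weeks is not a firm ceiling: Section 4.5.2 allows participation well beyond 18 weeks after the last dose, and Section 4.5.3.3 states no cap. What scanning takes place in that time is not in the SAP. A self-contradiction in the text, a fixed percentage loss and a bias between arms are not supported.

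**What to change.** In Section 4.5.3.3 of the placebo-controlled SAP, end follow-up at the last MRI assessment in the placebo-controlled period. In Section 3.5.3.3 of the LTE SAP, run it from the first active dose to the last MRI in the active treatment period. If the sponsor prefers the general definition, the section should say why it suits an event found only on MRI.

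The cost is one sentence in each SAP; the last-MRI date is already needed for the EAIR and the Kaplan-Meier censoring. The change aligns the end of observable follow-up and nothing more. The dilution of the recurrence rows by subjects and time not at risk is a separate matter. A recurrence proportion among subjects with a dose and a scan after the previous resolution, whose count is already planned, would address it.
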